All assessment and treatment providers will be trained and supervised by the Principal Investigator, who is a licensed psychologist (and with backup supervision coverage from [name], licensed psychologist). At intake, participants identified by clinical interview with suicidal ideation and acute intent will be excluded from the study and immediately offered emergency psychiatric care at the VAMC. During the duration of the study, the Principal Investigator (or covering Co-Investigator) will immediately contact the participant and assess suicide risk when any instance of suicide risk is identified (preferably before the participant leaves the appointment). If suicidal ideation is present but not intent, the participant will be retained in the study and reassessed for suicide risk by the investigators in one week. In cases of acute suicidal intent, state law requires immediate hospitalization and these guidelines will be followed.

Assessment of Quality of Life, Psychological Well-Being, Social Reintegration, Psychiatric Symptomatology, and Treatment Satisfaction

The battery of self-report questionnaires and a diagnostic interview will be completed pre-, mid-, and post-treatment and at the 6-month follow-up to track participants' progression through treatment and maintenance. The mid-treatment assessment will include the self-report questionnaires only (no diagnostic interview). Following the initial assessment at pre-treatment, all assessment sessions will be completed either in-person and via VA-approved telehealth technologies, based upon the preference of the participant. These time points for the assessments are consistent with CBT research with Veterans with depressive/anxiety disorders, as well as with the Pl's CDA. Participants will be compensated \$40 for pre-treatment, \$60 for mid-treatment, \$80 for post-treatment, and \$120 for 6-month follow-up for completion of assessment procedures for a total of \$300 for the entire study. To reduce the likelihood of missing data, all assessments will be scheduled separately from normal treatment sessions. Assessments of quality of life, social reintegration, and general symptoms of the depressive/anxiety disorders, rather than multiple disorder-specific questionnaires, were chosen due to the

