transdiagnostic approach and related research aims of the proposed study. In addition, participants will be asked to voluntarily solicit a friend or family member to complete a collateral report on a measure of functioning (IIRS). Procedures for adapting and analyzing the collateral report will follow previously published investigations of self-other assessments by the study team ([name] et al., 2010; Simms et al., 2010). All assessments will be completed by the Project Research Recruiter and Assessor. Additional training will be required prior to administration of the diagnostic interview (ADIS-5). The assessor will be required to observe the PI administer the ADIS-5 twice and then administer the ADIS-5 twice themselves under the direct observation of the PI. The assessor will be blinded to treatment condition and supervised by the PI. ADIS-5 assessments will be recorded to investigate inter-rater reliability of diagnoses, with 20% of recordings being re-assessed by an external ADIS-trained assessor after the participant has completed all study procedures, with feedback provided to the assessor throughout the duration of the study to improve reliability. In addition to the four assessment points, select measures (PHQ-9 and PCL-5) will be administered every other treatment session to monitor safety and treatment progress.

Albany Panic and Phobia Questionnaire (APPQ). The APPQ is a 27-item self-report measure that assesses agoraphobia, social anxiety, and interoceptive avoidance (Rapee et al., 1994/1995). Each subscale has been shown to have good internal consistency (α s > .85) and temporal stability (rs > .87) (Brown et al., 2005).

Anxiety Disorder Interview Schedule-5 (ADIS-5). The ADIS-5 is a semi-structured interview designed to assess a wide range of Axis I disorders (Brown, 2014). The ADIS-5 assesses current and past diagnoses with DSM diagnostic criteria, severity scores, and lists of feared and avoided situations for the anxiety disorders. The ADIS-5 has demonstrated excellent inter-rater reliability and validity of depressive/anxiety disorder diagnoses.

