The continuous measures of quality of life, psychological well-being, and social reintegration are CHART (disability), CRIS and CHART (social reintegration), IIRS and V/SF-36 (quality of life and impairment), APPQ (agoraphobia, social anxiety, and interoceptive avoidance), DASS (depression, anxiety, and stress), ADIS-5 (disorder dimensional severity scales), PCL-5 (PTSD), and STICSA-Trait (cognitive and somatic anxiety). Although multiple variables will be examined, the primary outcomes of interest will be IIRS, PCL-5, and DASS depression scores. All other analyses will be conducted in an exploratory fashion to inform future studies. Parameter estimates to calculate the effect size difference will be arrived at using three-level (measurement occasions nested within participants nested within assigned treatment group) generalized mixed-effects regression models (MRM). MRM is a method of repeated measures analyses that allows for modeling of continuous and categorical independent and dependent variables and for appropriate modeling of covariance structures when observations are correlated across time and/or across group. This analytic approach fully captures variability in outcomes across multiple follow-up assessments and accounts for any potential effect of the group to which a participant is assigned and is thus preferred over methods that collapse data over time. We will calculate between-group treatment differences as the d, based on the effect of treatment condition on the intercept parameter when the model is centered on post-intervention and on the effect of treatment condition on the intercept parameter when the model is centered on month 6. We prespecified the non-inferiority margin (d) to be 0 (indicating we expected G-TBT to be at least equivalent to G-DST) and the one-sided CI for our three primary analyses at $\alpha = .0008$. In the primary analyses of outcome variables, we will covary for the baseline value of the variable of interest. We will also include the linear effect of time as well as a time by condition interaction effect to determine whether treatment differences (or lack thereof) were stable from post-intervention through the follow-up. Additional covariates (e.g. age, number of psychiatric comorbidities, race, sex, combat theatre, and number of treatment sessions) will be added to the model to adjust for putative confounding variables. Effect size CIs that do not contain 0 provide evidence in support of noninferiority for G-TBT.

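### Does the linear-time model, which does not list its outcome occasions, blur the post-treatment d?

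*Combined protocol and SAP*

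**What the plan says.** Non-Inferiority Analyses (Primary Aim 1) describes a three-level mixed model: occasions within participants within treatment groups. The baseline value of the outcome is a covariate. The between-arm d is "based on the effect of treatment condition on the intercept parameter when the model is centered on post-intervention", and again with centring on month 6. On time, the section states: "We will also include the linear effect of time as well as a time by condition interaction effect". The purpose given is "to determine whether treatment differences (or lack thereof) were stable from post-intervention through the follow-up". The section also says that the approach "is thus preferred over methods that collapse data over time". It does not list the occasions that supply outcome data, and it does not say how time is coded.

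The assessment section (headed Assessment of Quality of Life, Psychological Well-Being, and so on) says that the battery "will be completed pre-, mid-, and post-treatment and at the 6-month follow-up". At mid-treatment only the questionnaires are given, without the ADIS-5 interview. It adds: "In addition to the four assessment points, select measures (PHQ-9 and PCL-5) will be administered every other treatment session". The purpose stated for those extra scores is to monitor safety and progress.

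**The concern.** IIRS, PCL-5 and DASS depression are all self-report, so each has a mid-treatment score, and no sentence keeps those scores out of the model. With three occasions, a straight line in time cannot pass through three arbitrary arm differences. The condition effect at the post-intervention centring would then borrow from mid-treatment and month 6. It would no longer be the post-treatment difference unless the arm difference happened to be linear in the chosen time metric. That would sit badly with a method chosen because it does not collapse over time.

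The stakes would be real because the margin is d = 0, which puts equality on the null boundary. A G-TBT lead at mid-treatment that had vanished by the end of treatment could carry the post-treatment d above zero, with no reversal of sign needed.

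**Working it through.** **The plan's own figure.** Sample Size Determination gives 76 per cell for d = 0.60, margin 0, 90% power and a one-sided .025/3. Check: 2 × (2.394 + 1.2816)² / 0.60² = 75.05, which rounds up to 76. (The printed .0008 is not .025/3 = .0083 and would need 110 per cell. That is a separate matter, and .025/3 is used below.) So 76 is a single-time comparison of two means, with no credit taken for repeated measures.

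**Inputs and assumptions.** The 12 weekly sessions come from Procedures. Assumed: mid-treatment at week 6, post-treatment at week 12, 6-month visit at week 38 (or week 26), complete data after multiple imputation, equal variances, and a common within-person correlation ρ of .4 to .6. Positive differences favour G-TBT.

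**Weights.** In a linear time-by-condition model with k occasions, the condition effect at centring time t0 gives occasion i the weight

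w_i = 1/k + (t0 − t̄)(t_i − t̄)/Sxx.

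*Two occasions, t = (12, 38), t0 = 12.* t̄ = 25 and Sxx = 338.
- Post weight: .5 + (−13)(−13)/338 = 1.
- 6-month weight: .5 + (−13)(13)/338 = 0.

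Centring on month 6 gives 0 and 1. In a three-level simulation (20 groups of 8, 400 runs), linear and categorical time gave the same mean d (.309) and the same standard error (.1686). The largest discrepancy was 5 × 10⁻¹⁶.

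*Three occasions, t = (6, 12, 38), t0 = 12.* t̄ = 18.67 and Sxx = 578.67.
- Mid: .333 + 84.44/578.67 = .479.
- Post: .333 + 44.44/578.67 = .410.
- 6-month: .333 − 128.89/578.67 = .111.

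| Coding and correlation | Mid | Post | 6-month |
|---|---|---|---|
| Weeks 6/12/38, common | .479 | .410 | .111 |
| Weeks 6/12/26, common | .443 | .367 | .190 |
| Visit number, common | .333 | .333 | .333 |
| Visit number, AR(1) .5 | .40 | .20 | .40 |
| Weeks 6/12/38, autoregressive .8 per 6 weeks | .66 | .19 | .15 |

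**What the mixing could do (three occasions, weeks 6/12/38, common correlation).** True differences of .3/0/0 give a post d of .479 × .3 = .144. The single-time standard error is √(2/76) = .162. The ratio of linear to categorical standard error is √((1 − ρ)Σw² + ρ), with Σw² = .410, which is .804 at ρ = .4 and .874 at ρ = .6.
- ρ = .4: Φ(.144/(.162 × .804) − 2.394) is about 10%.
- ρ = .6: Φ(.144/(.162 × .874) − 2.394) is about 8%.

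The nominal rate is .83%.

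**What categorical time would cost (three occasions).** If the difference is truly linear, the categorical standard error is larger by 1/.874 − 1 = 14% to 1/.804 − 1 = 24% at weeks 6/12/38. It is 16–27% larger with follow-up at week 26 and 17–29% larger by visit number. With a constant difference of 0.60 (the figure used in the sample-size arithmetic, not a forecast between-arm gap), power at weeks 6/12/38 is 97–99% with linear time and 90% with categorical time.

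**Break-even.** Let D be the post-treatment difference minus the straight line joining the mid and 6-month differences. At a post-treatment difference of 0.60, categorical time has more power once D exceeds .60 × (1 − ratio)/(1 − .410). That is .200, .163 and .128 for ρ = .4, .5 and .6. The documents hold nothing that locates D.

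**Which reading fits the text.**
- Baseline is adjusted for, and the plan does not call it an outcome occasion.
- Only two centrings are named, post-intervention and month 6.
- The interaction is there to judge stability between those same two points.
- The same model is applied to the ADIS-5 severity scales, which have no mid-treatment value.
- The assessment section gives the battery a further use, following participants through treatment, so collecting a mid-treatment score does not imply modelling it.

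**The case for a change.** The strongest case for acting is that the purpose of an interaction term is not a list of included data. Two analysts could read the section, one fit two occasions and the other three, and report different post-intervention values of d for a primary outcome. With calendar coding the second analyst's estimate would weight mid-treatment most heavily. PCL-5 has session-level scores too: if those entered (assumed weeks 2, 4, … 12, and 38), the week-12 score would carry only about .14 of its own estimate. Listing the occasions would take one sentence, and the planned sample never relied on the precision that linear time brings.

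What stands is that the occasions are not listed and that three occasions would produce the mixing shown. It remains conditional, however. It needs an analyst to choose the reading that fits the section less well, and then an arm difference that departs from a line in time. The session-level PCL-5 scores are described as monitoring on top of the four assessments, so treating them as outcomes is further still from the text. Categorical occasion would change nothing under two occasions. Under three it could gain or lose power, depending on a trajectory nobody can state in advance.

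**Conclusion.** No change follows. On the reading that the section best supports, with post-treatment and 6-month outcomes and baseline as covariate, the linear-time model estimates exactly the two differences it names, and categorical time would give the same d and standard error. This rests on time being coded at nominal visits; with actual elapsed days the two models would differ slightly. If mid-treatment scores were modelled, the post-treatment d would be a blend, and .3/0/0 would be declared non-inferior about 8–10% of the time instead of .83% (76 per cell, ρ of .4 to .6, weeks 6/12/38, common correlation). Against that stands the 14–29% larger standard error of the alternative when the difference is linear. The weights themselves move with the time coding and the covariance structure, so these figures illustrate a possibility and do not document a loss. The unlisted occasions are a gap in detail that the surrounding text already fills.

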
Eligibility Criteria

Inclusion criteria: 1) participants must be clearly competent to provide informed consent for research participation, 2) participants must meet DSM-5 criteria for either MDD or PTSD, and 3) participants must be 18 -80 years of age. Exclusion criteria involve: 1) recent history (≤ 2 months) of psychiatric hospitalization or a suicide attempt and/or suicidal ideation with acute intent as documented in their medical record or reported during clinical interview, 2) current diagnosis of substance use disorder as documented in their medical record or reported in clinical interview, 3) acute, severe illness or medical condition that likely will require hospitalization and/or otherwise interfere with study procedures as documented in their medical record (e.g., active chemotherapy/radiation treatment for cancer), 4) recent start of new psychiatric medication (< 4 weeks), 5) diagnosis of traumatic brain injury (TBI) in their medical record and/or endorsement of screener questionnaire (McAllister et al., 2016), or 6) diagnosis of schizophrenia, psychotic symptoms, and/or bipolar disorder as documented in their medical record or reported in clinical interview. Additional comorbid psychiatric diagnoses that were not listed as exclusion criteria are permitted as long as they are considered secondary to the principal diagnosis of MDD or PTSD as determined by the diagnostic interview. Of note, if participants request changes to their psychiatric medications at any time during the treatment, a medication consult will be completed with a prescriber in VA Mental Health. Any changes in medications and/or initiation of non-study psychotherapy will be recorded for inclusion in the analyses as a possible covariate. Ineligible Veterans will be referred for non-studyrelated treatments within mental health at the RHJ VAMC.

Procedures

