Eligible VAMC patients will be randomized into one of two treatment conditions: G-TBT or G-DSTs. Both treatment conditions will include 12 weekly 90-minute group sessions. Both treatment conditions will be delivered either in-person and via VA-approved telehealth technologies, based upon the preference of the participant and the group schedule. The general format of sessions will involve: 1) brief check-in; 2) review of materials from previous sessions; 3) review of homework assignments; 4) overview of new materials and in-session exercises; and 5) assignment of homework for next session. Attendance and homework completion will be recorded.

Randomization Procedures

Participants will be randomly assigned (1:1) to one of the two study arms (n = 163 per arm) using a permuted block randomization procedure. Randomization will be stratified by principal diagnostic group (or most impairing disorder between MDD and PTSD if both disorders are present, based upon ADIS disorder-specific interference and distress severity scores) and block size will be varied to minimize the likelihood of unmasking. If both disorders evidence identical severity scores (highly unlikely), participants will be asked which of the two disorders is more impairing/significant for randomization purposes. After determining eligibility and completing consent and baseline assessment materials, enrolled participants will be assigned to treatment conditions by the Research Coordinator/Therapist using a computer-generated randomization scheme. Once a participant is randomized, they will be included in the intent-to-treat analysis. The Research Coordinator/Therapist, and the statistical analyst in charge of randomization ([name]) will be the only research team members aware of the randomization assignment. Randomization will occur at the participant level. As such, we will take the following steps to minimize contamination between the two arms of the study: 1) only one member of a household will be eligible for enrollment; and 2) other VA providers will be informed of their patients' participation in the study, but will be blinded to the treatment condition.

Group Transdiagnostic Behavior Therapy

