Feasibility and Acceptability Analyses (Primary Aim 2)

Measures of feasibility and acceptability are discontinuation proportions (discontinuation y/n), proportion of sessions attended, proportion of homework assignments completed, wait-time from baseline to start of the group treatment (access, measured in days), and patient satisfaction scores on the STTS-R. Frequency distributions describing the participants' reasons for noncompliance and discontinuation of participation will be developed. Because feasibility and acceptability analyses involve changes from baseline to post-intervention only and several of the outcomes are categorical, the generalized linear mixed model (GLMM) framework will be used to compare G-TBT to G-DST on treatment satisfaction, retention (discontinuation), and treatment adherence (% missed sessions, % homework completion). Discontinuation proportions (dichotomous outcome), % of missed visits, and % homework completion will be compared between the intervention groups using GLMM, with logistic/binomial regression analyses as special cases for dichotomous and percentage outcomes; access and STTS-R will be modeled as a continuous outcome using an appropriate link function. We also will model the longitudinal profile of adherence as a dichotomous outcome at each visit (e.g. attended/did not attend a given session). This will allow us to evaluate the trends in session attendance and to determine if the trends differ by intervention (e.g. whether the probability of missing visits is less/greater at earlier or later time points).

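### The Aim 1 non-inferiority model adjusts for number of treatment sessions, which arises after randomisation and can bias the comparison if the arms differ in attendance

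*Combined protocol and SAP*

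**What the plan says.** The section Non-Inferiority Analyses (Primary Aim 1) describes a three-level mixed model with the baseline value of the outcome, time, and time by condition. It then continues: "Additional covariates (e.g. age, number of psychiatric comorbidities, race, sex, combat theatre, and number of treatment sessions) will be added to the model". The stated purpose is to adjust for presumed confounding. The decision rule follows at once: "Effect size CIs that do not contain 0 provide evidence in support of noninferiority for G-TBT". The margin is d = 0.

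Four other places bear on this:

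- **Procedures:** "Both treatment conditions will include 12 weekly 90-minute group sessions". The same section adds: "Attendance and homework completion will be recorded".
- **Feasibility and Acceptability Analyses (Primary Aim 2):** "Discontinuation proportions (dichotomous outcome), % of missed visits, and % homework completion will be compared between the intervention groups using GLMM". The section also plans to test whether attendance trends differ between the interventions.
- **Randomization Procedures and Missing Data:** everyone randomised belongs to the intention-to-treat set. Completer and per-protocol analyses are sensitivity checks.
- **Eligibility Criteria**, on events during treatment: "Any changes in medications and/or initiation of non-study psychotherapy will be recorded for inclusion in the analyses as a possible covariate". The analyses meant are not named.

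**The concern.** A confounder of a randomised comparison would have to be a common cause of assignment and outcome. With 12 sessions planned in both arms, the number a participant receives is settled only after assignment. It may be a consequence of assignment, and Aim 2 exists partly to find out. The other covariates named can be taken at baseline; this one cannot.

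Holding attendance constant does two things. It removes any part of the treatment effect that runs through attendance. If an unmeasured factor drives both attendance and outcome, it also opens a non-causal path between arm and outcome (collider bias). Either way, the estimate is no longer the effect in all randomised participants.

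When more sessions go with better outcome, the adjustment favours the arm that is attended less. At a margin of d = 0 nothing absorbs such a shift. It can create a non-inferiority finding if G-TBT is attended less, or hide one if G-TBT is attended more.

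**Working it through.** **The plan's own figures.** The point turns on no stated number, but alpha and the effective sample size enter the illustration.

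- n per arm = 2(z₁₋α + z₁₋β)²/d². With α = .025/3 = .00833, 90% power and d = 0.60: 2(2.394 + 1.282)²/0.36 = 75.1, so 76 per arm (152), as stated.
- The printed .0008 would need 110 per arm, so .0083 is the alpha that fits the stated size. Results below use .0083, with .0008 where available.
- Clustering gives 152 × (1 + 7 × .025) = 178.6, against 174 stated. Then 174 × 1.37/0.73 = 326.5, matching 326. The information planned for is therefore about 174/2 = 87 per arm.

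None of these figures depends on the session covariate.

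**Size of the shift.** Code d so that positive favours G-TBT. In a linear model,

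shift in d = −(difference in mean sessions, G-TBT minus G-DST) × (within-arm slope of outcome on sessions, in outcome SDs per session).

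The slope equals correlation/SD of sessions. The documents give neither, so I assumed sessions bounded 0 to 12, mean 7.9, SD 3.3 and correlation about 0.2 to 0.4.

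- One session: 0.2/3.3 = 0.06 to 0.4/3.3 = 0.12.
- Two sessions: 0.12 to 0.24 by the formula.
- No difference in sessions, or zero slope: 0.

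A large-sample simulation (400,000 per scenario; an unmeasured factor affecting attendance and outcome; total d set to 0) gave, with G-TBT attended more:

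| Correlation | 1-session difference | 2-session difference |
|---|---|---|
| 0.19 | −0.06 | −0.13 |
| 0.30 | −0.09 | −0.19 |
| 0.39 | −0.12 | −0.25 |

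With no difference in sessions the adjusted d was 0.00 throughout.

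**Effect on the decision.** Trial-size simulation: 12,000 trials per scenario, 160 per arm in groups of 8, ICC .025, complete data, one post-treatment occasion, baseline covariate. The ranges run from the weakest to the strongest correlation above.

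| Scenario | One-sided alpha | Without sessions | With sessions |
|---|---|---|---|
| True d = 0, G-TBT 1 session fewer | .0083 | 0.8% | 3.4% to 12.4% |
| True d = 0, G-TBT 1 session fewer | .0008 | at most 0.1% | 0.4% to 3.2% |
| True d = 0, equal sessions | .0083 | – | 0.7% to 0.95% |
| True d = 0.30 (assumed), G-TBT 1 session more | .0083 | about 65% | 30% to 45% |

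**A second set of inputs.** A separate simulation used 163 per arm without clustering, a direct slope of 0.3 per SD of sessions, and an unmeasured factor with coefficient 0.4 on both sessions and outcome. The within-arm slope is then 0.3 + 0.4 × 0.4 = 0.46. A 0.3 SD difference (about 0.3 × 3.3 = 1 session) shifts the estimate by 0.3 × 0.46 = 0.14. False non-inferiority at .0083 was about 1% without sessions in the model. With sessions it was 20% at 0.3 SD lower G-TBT attendance, 57% at 0.5 SD lower, and 0% at 0.3 SD higher. It was unchanged when attendance was equal.

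**The case against.** **The covariate may not be in the decision model.** One can read the section stepwise: a primary model with baseline, time and interaction, then an extended model. Nothing labels the extended model secondary, however, and the decision rule comes directly after it. On the stepwise reading there would still be no statement of which model decides.

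**The term is undefined and the list opens with e.g.** It might mean sessions delivered to a group and not sessions attended. That is also post-randomisation. An illustrative list still names this variable as one that will be added.

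**The error rates assume complete data.** This stands. The plan expects information nearer 87 per arm. A rerun of the same data model at 88 per arm gave about 2.1% and 7.1% in place of 3.4% and 12.4%. Rescaling the power figures by √(87/160) = 0.737 works as follows: 65.2% corresponds to 2.394 + 0.391 = 2.785 standard errors; 2.785 × 0.737 − 2.394 = −0.34, or about 37%. The adjusted 45% and 30% become about 23% and 15% in the same way. The pattern is unchanged and the absolute figures are lower.

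**All attendance inputs are assumed, and the bias may be zero or work against G-TBT.** This also stands, and the figures show only what is possible. The false-positive scenarios in the working also need a direct G-TBT benefit that exactly offsets lower attendance. The bias itself does not need that offset. With no effect of sessions on outcome, a true effect of zero and G-TBT attendance 0.5 SD higher, the unmeasured factor alone moved the adjusted estimate to −0.08. By the formula, 0.5 SD lower attendance gives +0.08.

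**Conclusion.** The point holds. Number of treatment sessions is post-randomisation on any reading the documents support. Using it as a confounder adjustment in Aim 1 conflicts with the intention-to-treat commitment and with its role as an Aim 2 outcome. The completer and per-protocol comparisons do not cure this, because they change the analysis set and leave the covariate in the model.

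The bias is conditional: it needs arm to affect attendance, and attendance or its unmeasured causes to relate to outcome. If both hold, a one-session difference plausibly moves d by about 0.06 to 0.12 under the assumed SD and correlations, in favour of the less-attended arm when attendance goes with better outcome. True size and direction cannot be known from the documents. Because the variable may enter the model that decides the primary aim, it should be corrected before outcomes by arm are examined.

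The medication and non-study psychotherapy variables raise the same question less sharply. The plan calls them only possible covariates in unnamed analyses, so they need clarification and are not shown to be an error.

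**What to change.** 1. Delete number of treatment sessions from the Aim 1 covariate list.
2. Name one model per primary outcome as the basis of the non-inferiority decision. Close its covariate list and restrict it to values known before randomisation: baseline score, age, sex, race, combat theatre and baseline comorbidity count. The principal-diagnosis stratum fits here too, since it is a stratification factor, although the correction does not depend on it.
3. Use sessions attended in Aim 2, as an auxiliary variable in the imputation model, or in a dose or mediation analysis labelled as supplementary.
4. State that medication changes and non-study psychotherapy begun during the trial stay out of the primary model and are used only descriptively or in labelled secondary analyses.

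The cost is SAP wording. No data collection is lost and no sample-size figure changes.
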